7 MEDICINAL PRODUCT AND DEVICE

7.1 Description of medicinal product

Neupro (rotigotine) is a nonergolinic dopamine agonist for the treatment of the signs and symptoms of Parkinson's disease and Restless Legs Syndrome (RLS). Neupro elicits its beneficial effect on Parkinson's diseases by activation of the D3, D2 and D1 receptors of the caudate-putamen in the brain.

Neupro (Anatomical Therapeutic Chemical [ATC] code: N04BC09) is available as a transdermal system in six dosages. In the current study, Neupro is to be applied as prescribed by the Investigator and based on instructions provided in the patient leaflet/package insert (NEUPRO [package insert], 2016 [[Section 15](#)]).

7.2 Devices

In the present study, all subjects will use the Kinesia-ONE device in-clinic during the Screening Visit for specific motor tasks/for recording of specific baseline motor symptoms. Subjects randomized to the Experimental Group will also use the Kinesia-360 device at home for continuous measurement of motor symptoms.

Kinesia-360 is intended to monitor physical motion and muscle activity to quantify kinematics of movement disorder symptoms such as tremor, and assess activity in any instance where

quantifiable analysis of motion and muscle activity is desired. Kinesia Regulatory Certifications: Kinesia-One and Kinesia-360 have received US Food and Drug Administration (FDA) 510K clearance to market (06 Apr 2007), Conformité Européen Mark (European Medical Device Directive 93/42/EEC), Canadian Medical Device Conformity Assessment Systems, Australian Therapeutic Goods Association Certification, and International Organization for Standardization (ISO) 13485 (2003). Kinesia-One and Kinesia-360 are tested to International Electrotechnical Commission 60601 Standards, comply with Federal Communications Commission Part 15 Rules, and are Health Insurance Portability and Accountability Act compliant, and FDA Part 11 compliant for Electronic Data Capture in Clinical Trials.

7.2.1 Description of devices

Kinesia-ONE Wearable Sensor uses a subject-worn finger sensor and iPad mini application (APP) to objectively measure specific motor tasks related to Parkinson’s disease symptoms such as tremor, bradykinesia (slowed movements), and dyskinesia (involuntary movements) in the Investigator’s office. Subjects should wear the Kinesia-ONE device on the most affected side.

Kinesia-360 Wearable Sensor includes a wrist and ankle device, along with a cell phone, which is also APP-based, and is designed for continuous day time monitoring of Parkinson’s disease symptoms. Subjects will wear Kinesia-360 while they go about their daily lives, and symptom severity is continually captured to enable objective assessment of Parkinson’s disease symptoms. Subjects should wear the Kinesia-360 device bands on the most affected side.

Symptom data recorded by either device, as well as the corresponding data reports, will be made available to the Investigators through a web portal.

The following variables will be derived from either Kinesia device to be used in PD0049:

Kinesia-ONE	Kinesia-360
Change from Baseline to Visit 2 (Week 12) in the following Kinesia-ONE measures, which will be averaged from triplicate repeated assessments at a measurement point:	Change from Baseline to Visit 2 (Week 12) in the following Kinesia-360 measures, which will be averaged from 2 consecutive days of wear:
Resting tremor score	Average daily tremor score
Postural tremor score	Average daily slowness score
Finger tapping speed and amplitude scores	Average daily dyskinesia score
Hand grasps speed and amplitude scores	% wear-time tremor was detected
Rapid alternating movements speed and amplitude scores	% wear-time dyskinesia was detected
Dyskinesia score	% wear-time user was not moving
	% wear-time user was walking

	% wear-time user was active, but not walking
	Number of steps/h while wearing the device

7.2.2 Packaging and labeling of the Kinesia devices

The sites will receive uniquely numbered wearable sensor devices (Kinesia-ONE and Kinesia-360) for use in the study. The devices will be provided in the intended final packaging.

7.2.3 Storage requirements

Sensor devices must be stored in a secured area with limited access at the Investigators' sites.

7.2.4 Device accountability

Great Lakes Neuro Technologies, Inc. (GLNT) will supply the wearable sensor devices and associated equipment / software. The Investigator must ensure that the devices are used only in accordance with the manufacturer's instructions. A device accountability form will be used to record the receipt and return dates of the wearable sensor devices and associated equipment/ software. In addition, dispensing and returning information on a by-subject basis will be completed. This form will serve as source documentation during the course of the study. Details of any device lost, not used, disposed of at the study site, or returned to the Sponsor must also be recorded. The Investigator, after completion of the study, will ensure that all devices are returned to GLNT.

7.3 Concomitant medications/treatments

Subjects will continue with their usual treatment. All medications/treatments (ie, Parkinson's disease medications and others), including dosages, will be recorded in the appropriate study documents (ie, eCRF and source document).

Investigators are encouraged to adjust, if needed, the Neupro dose to optimize Parkinson's disease symptoms. Back-titration of the Neupro dose in case of AEs is allowed as per standard of care.

Subjects are encouraged not to change the dosages of any concomitant medications during the study. There are no prohibited medications defined for this study.

7.3.1 Rescue medication

Not applicable.

7.4 Blinding

Not applicable.

7.5 Randomization and numbering of subjects

Subjects will be randomized (1:1) to either the Control Group (without Kinesia-360 device to measure motor symptoms at home) or the Experimental Group (with Kinesia-360 device to measure motor symptoms at home) during the Screening Visit (Visit 1). The randomization will be stratified by site. A randomization list for each site with a block size of 4 will be provided to

the site. Each subject will receive a 5-digit number assigned at Screening that serves as the subject identifier throughout the study.

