5 STUDY DESIGN

5.1 Study description

PD0049 is a multicenter, open-label, two-arm, 12-week study in subjects with Parkinson's disease. On Day 1, eligible subjects will be randomized to either the Control Group or the Experimental Group in a 1:1 fashion. In both groups, subjects will use the Kinesia-ONE wearable device in-clinic at Visit 1 and Visit 2 for recording of specific motor symptoms, and subjects randomized to the Experimental Group will also use the Kinesia-360 wearable device at home while awake for continuous measurement of motor symptoms. The Investigator will use these symptom data to provide feedback to subjects on their motor symptoms and to supplement standard of care to titrate the optimal dose of Neupro for any given subject. In the Control Group, subjects will not use any wearable device at home, and the Investigator will use only standard of care to titrate the optimal Neupro dose.

Subjects in the Control Group and the Experimental Group will start treatment with Neupro 2mg/24h or 4mg/24h (at the Investigator's discretion and according to the disease stage of the subject) preferably on Day 1 (but no later than Day 4) or Day 4, respectively. Evaluations conclude 12 weeks after the start of treatment with Neupro (ie, at Visit 2).

The decision to prescribe Neupro must be made by the Investigator independent of his/her decision to include the subject in the study. The subject's treatment/Neupro intake must be within the terms of the marketing authorization; Neupro will not be supplied by UCB.

A schedule of study assessments is presented in [Table 5-1](#); for a detailed rationale of the study design see [Section 5.3](#).

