5.1.2 Planned number of subjects and sites

This study will be conducted in approximately 6 sites and will include a total of approximately 40 subjects (20 subjects in the Experimental Group and 20 subjects in the Control Group). Of note, a single site will not randomize more than 20 subjects.

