6 SELECTION AND WITHDRAWAL OF SUBJECTS

6.1 Inclusion criteria

To be eligible to participate in this study, all of the following criteria must be met:

1. Subject is newly prescribed Neupro and is expected to commence Neupro treatment. Historical Neupro treatment is permitted.
2. An Institutional Review Board (IRB) approved written Informed Consent form (ICF) is signed and dated by the subject, before any study-related procedures.
3. Subject is considered reliable and capable of adhering to the protocol, visit schedule, completion of the diary, and using Kinesia devices according to the judgment of the Investigator.
4. Male or female subject, ≥ 18 years of age at the time of the Screening Visit.
5. Subject has Parkinson's disease, defined by the cardinal sign, bradykinesia, plus the presence of at least 1 of the following: tremor at rest, rigidity or impairment of postural reflexes, and without any other known or suspected cause of Secondary Parkinsonism.
6. Subject experiences motor symptoms associated with Parkinson's disease that are not sufficiently controlled by current therapy. The average of the triplicate resting tremor scores and triplicate finger tapping scores from Kinesia-ONE (6 scores in total) must be >1.0 .

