6.2 Exclusion criteria

Subjects are not permitted to enroll in the study if any of the following criteria is met:

1. Subject is currently participating in any study with an investigational medicinal product (IMP) or investigational device.
2. Subject has any medical, neurological or psychiatric condition (eg, previous stroke, bipolar disorder, dementia, hallucinations, psychosis or severe depression, and drug or alcohol abuse) which, in the opinion of the Investigator, could jeopardize or would compromise the subject's ability to participate in this study.

3. Subject with Deep Brain Stimulation (DBS) device implant.

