8.1 Visit 1 /Screening

The Screening examinations will be completed within 4 days, the first of which will take place at the study site (in clinic) and will include the following:

Day 1, in clinic:

- Sign ICF
- Control Group and Experimental Group: Subject wears Kinesia-ONE sensor on the most affected side in the clinic to measure specific motor tasks in triplicate. Calculation of the average of triplicate resting tremor scores and triplicate finger-tapping speed scores (ie, 6 scores in total) must be >1.0 for subject inclusion in the study.
- Verification of inclusion/exclusion criteria and collection of demographic data (including weight and height)
- PDQ-39
- Investigator performs UPDRS assessment
- Patient Engagement Questionnaire
- Randomization (Control Group [without Kinesia-360 device use at home]/Experimental Group [with Kinesia-360 device use at home])
- Experimental Group: Trained in-clinic on Kinesia-360 device (and sent home with the device)
- Control Group: Start treatment with Neupro as prescribed (preferably on Day 1, but no later than Day 4); record date and dose
- Control Group and Experimental Group: Recording of AEs and concomitant medications

8.2 Week 1

Day 2 and 3, home:

- Experimental Group: Subject wears Kinesia-360 wrist and ankle devices on Days 2 and 3 at home for baseline
- Experimental Group: Recording of concomitant medications and Neupro dose via APP

Day 4, home:

- Experimental Group: Start treatment with Neupro as prescribed; record date and dose via APP

- Experimental Group: Recording of concomitant medications

8.3 Weeks 2, 3, and 4

Control Group, home:

- Investigator uses standard of care to adjust Neupro dose as needed.
- Phone contact initiated by subject or Investigator as needed. Documentation of any contact or dosage adjustment.

Experimental Group, home:

- Subject uses Kinesia-360 at least on 2 consecutive days at home weekly to measure motor symptoms.
- Subject accesses Kinesia-360 motor symptom reports on device following each day of measurements.
- Investigator receives Kinesia-360 motor symptom reports via web portal following each day of measurements.
- Investigator combines standard of care with weekly Kinesia-360 motor symptom reports to adjust Neupro dose as needed.
- Phone contact initiated by subject or Investigator as needed and dispatch of Kinesia-360 motor symptom reports. Documentation of any contact or dosage adjustment.
- Recording of concomitant medications and Neupro dose via APP.

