9.1.1 Unified Parkinson's Disease Rating Scale

The change from Baseline to Visit 2 (Week 12) in Part III UPDRS Motor Score will be utilized as a primary efficacy variable.

The UPDRS is a comprehensive assessment of symptoms in subjects with Parkinson's disease. If possible, the same Investigator will perform both UPDRS assessments on a given subject. In PD0049, Parts I, II, and IV of the UPDRS will be used for the assessment of other efficacy variables.

9.1.2 39-Item Parkinson's Disease Questionnaire

Another efficacy variable to be assessed is the change from Baseline to Visit 2 (Week 12) in PDQ-39 questionnaire scores.

In Parkinson's disease, the PDQ-39 is the most widely used subject-reported rating scale endpoint in clinical studies.

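### Protocol 7.5 sends each site its own randomization list and prints a fixed block size of 4 in an open-label trial, and neither document describes a step that conceals the next assignment

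*Protocol*

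**What the plan says.** - **Allocation.** Protocol 7.5 randomizes 1:1 at Visit 1, stratified by site. "A randomization list for each site with a block size of 4 will be provided to" the site. SAP 2.3 and 3.6 repeat that subjects are randomized and add no mechanism.
- **Visibility.** Protocol 5.1: "PD0049 is a multicenter, open-label, two-arm, 12-week study". Section 7.4 marks blinding as not applicable, so past assignments at a site can be seen.
- **Judgement at entry.** Inclusion criterion 3 covers reliability and "using Kinesia devices according to the judgment of the Investigator". Exclusion criterion 2 covers conditions which, "in the opinion of the Investigator, could jeopardize or would compromise the" subject's participation.
- **Baseline rating.** In Protocol 8.1, "Investigator performs UPDRS assessment" on Day 1. The list in 8.1 places the eligibility check and this rating before randomization, but neither 8.1 nor 7.5 makes recording them a condition for releasing the assignment.
- **Size.** Protocol 5.1.2: "This study will be conducted in approximately 6 sites", with about 40 subjects and no more than 20 randomized at one site.
- **Analysis.** SAP 8.1.2 uses ANCOVA with baseline, center and group for change in UPDRS Part III and the Kinesia-ONE scores. It uses logistic regression with treatment and center for discontinuation of Neupro.

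**The concern.** Blinding and concealment are different safeguards. An open-label trial can still hide the next assignment, and that is what protects the choice of who enters. Here the text delivers the list to the site and says nothing about its custody, its form or how each assignment is released.

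Someone who knows or can guess the next arm could, without intending to, apply inclusion 3 or exclusion 2 more or less strictly, or score the baseline UPDRS differently. Reliability and ability to manage the devices could plausibly be related to staying on Neupro, which is one of the primary variables.

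Adjusting for baseline score and center does not remove a difference between groups in traits that are not measured. The discontinuation model does not even carry a baseline covariate.

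**Working it through.** The plan states no figure on this point, so there is nothing to reproduce. The check asks how predictable the assignments are under Protocol 7.5 as written.

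**Inputs.** Block size 4, 1:1, one list per site (7.5); past assignments visible (5.1); about 40 subjects at about 6 sites, at most 20 per site (5.1.2). Site sizes of 7, 7, 7, 7, 6 and 6 are an assumption.

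**Case A, list readable at the site.** All 40 of 40 assignments are known.

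**Case B, list hidden, block size known.** A 2:2 block has 6 equally likely orders.

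| Position in block | Certain | Best guess correct |
|---|---|---|
| 1 | 0 | 1/2 |
| 2 | 0 | 2/3 |
| 3 | 1/3 | 2/3 |
| 4 | 1 | 1 |
| Sum per block | 4/3 | 17/6 |

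- Complete blocks: certain (4/3)/4 = 33.3%, guessable (17/6)/4 = 70.8%. Over 40 subjects that is 13.3 and 28.3.
- Site of 7 (one block plus three): certain 4/3 + 1/3 = 5/3; guessable 17/6 + 11/6 = 14/3.
- Site of 6 (one block plus two): certain 4/3; guessable 17/6 + 7/6 = 4.
- Assumed sites: certain 4 × 5/3 + 2 × 4/3 = 9.33 of 40 (23.3%); guessable 4 × 14/3 + 2 × 4 = 26.67 of 40 (66.7%).

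An unpredictable sequence would give 0% and 50%. Always naming the arm with fewer subjects so far at the site gives the same guess rate without knowing the block size. Removing the block size from the text therefore takes away certainty, not guessing.

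**What a controlled release would gain at the assumed sites.** If the list is now readable, predictability falls from 100% to 67%. If custody is already sound, it stays at 67% and nothing is gained.

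**Varying the block size** (full enumeration, sizes equally likely, guesser knows the possible sizes).

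| Scheme | Certain, assumed sites | Guessable, assumed sites | Guessable, site of 4 |
|---|---|---|---|
| Fixed 4 | 9.33/40 (23.3%) | 26.67/40 (66.7%) | 70.8% |
| {4,6} | 2.70/40 (6.8%) | 26.47/40 (66.2%) | 65.4% |
| {2,4} | 3.50/40 (8.7%) | 27.75/40 (69.4%) | 70.8% |

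Both mixed schemes reduce certainty at the assumed sites. Their effect on guessing depends on site size. With {4,6} the largest possible difference between arms at a site of 7 rises from 1 to 3, because a block of 4 can be followed by three like assignments from a block of 6. The expected difference moves from 1.00 to 1.05 at a site of 7 and from 0.67 to 0.37 at a site of 6.

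**What a baseline comparison could show afterwards.** A two-sample t test with 20 per arm, two-sided 0.05, has 80% power only at a difference of 0.91 SD.

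**The case against.** The strongest reply is that this is silence, not demonstrated exposure. Sending a list to a site does not mean enrolling staff can read it, and site documents outside the protocol and SAP may settle custody. That stands. A reader might infer that staff knew the assignments or that selection took place; the documents show neither.

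Three features also limit the exposure. Protocol 5.1 states "The decision to prescribe Neupro must be made by the Investigator independent of his/her decision to include" the subject. The Kinesia-ONE entry threshold and scores are device-measured. Section 8.1 lists eligibility and UPDRS ahead of randomization. Each helps, but none hides the next assignment from the person deciding inclusion.

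A reader might also infer that a release step is certain to bring a large gain. It is large only if the list is readable now. Nor does one assumed site layout justify ruling out a block scheme such as {2,4}: at a site of 4 it is no more guessable than fixed blocks.

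Finally, this is a pilot with no formal sample size (Protocol 12.8) and exploratory tests (Protocol 12.2, SAP 4.5). That lowers the stakes. It does not make the gap harmless, because the stated purpose is to gain an impression of the device's effect, and selection could distort that impression whatever status the p-values have.

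**Conclusion.** The point holds as a gap in the described method that should be fixed. Followed as written, Protocol 7.5 leaves assignments at least partly predictable: 33% certain and 71% guessable in complete blocks, 23% and 67% at the assumed sites, and 100% known if the list is readable. The hidden-list figures assume that staff know the block size and see all earlier assignments at their site. The second pair also assumes six sites enrolling 6 to 7 each.

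These are measures of opportunity. The documents give nothing that converts predictability into bias in a study estimate, so no such bias is claimed. A reader might take this as invalidating a confirmatory result. There is no confirmatory claim to invalidate; the effect is to limit how far the group estimates can be trusted.

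Concealment would also leave a separate exposure untouched. Under Protocol 9.1.1, "If possible, the same Investigator will perform both UPDRS assessments on a given subject", so the Visit 2 rater may know the group.

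**What to change.** **Before randomization.** Amend Protocol 7.5 so that the sponsor or CRO holds the list. Release each assignment singly (through the eCRF, by phone or email, or in sequentially numbered opaque sealed envelopes) only after eligibility, Kinesia-ONE and the baseline UPDRS are recorded. Remove the block size from the site-facing protocol. Varying the block size is optional: weigh the loss of certainty against the possible within-site imbalance at the site sizes expected.

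The cost is a short amendment, a release step for about 40 assignments and a short wait at Visit 1. No extra subjects, visits or assessors are needed.

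**For subjects already randomized.** SAP 13.1 says Amendment 1 followed the Data Evaluation Meeting, so this may be most or all of them. Record who held each site's list and in what form, and state the limitation in the report. If the record shows sound custody, the main worry is answered, though guessing from past assignments remains.

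The baseline summaries by group that the SAP already plans can be read, but only for gross imbalance. Medical history is not collected (SAP 6.3), so the conditions behind exclusion 2 are not directly visible. Disease stage is inferred from the starting dose (SAP 6.2), which the Investigator chooses (Protocol 5.1). These steps describe the risk and cannot undo it.

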8 STUDY PROCEDURES BY VISIT

Prior to the start of any study-related examinations or procedures, the written ICF must be signed and personally dated by the subject. The person (Investigator [or designee]) who conducted the informed consent discussion will document their informed consent process with his/her signature.

8.1 Visit 1 /Screening

The Screening examinations will be completed within 4 days, the first of which will take place at the study site (in clinic) and will include the following:

Day 1, in clinic:

- Sign ICF
- Control Group and Experimental Group: Subject wears Kinesia-ONE sensor on the most affected side in the clinic to measure specific motor tasks in triplicate. Calculation of the average of triplicate resting tremor scores and triplicate finger-tapping speed scores (ie, 6 scores in total) must be >1.0 for subject inclusion in the study.
- Verification of inclusion/exclusion criteria and collection of demographic data (including weight and height)
- PDQ-39
- Investigator performs UPDRS assessment
- Patient Engagement Questionnaire
- Randomization (Control Group [without Kinesia-360 device use at home]/Experimental Group [with Kinesia-360 device use at home])
- Experimental Group: Trained in-clinic on Kinesia-360 device (and sent home with the device)
- Control Group: Start treatment with Neupro as prescribed (preferably on Day 1, but no later than Day 4); record date and dose
- Control Group and Experimental Group: Recording of AEs and concomitant medications

8.2 Week 1

Day 2 and 3, home:

- Experimental Group: Subject wears Kinesia-360 wrist and ankle devices on Days 2 and 3 at home for baseline
- Experimental Group: Recording of concomitant medications and Neupro dose via APP

Day 4, home:

- Experimental Group: Start treatment with Neupro as prescribed; record date and dose via APP

- Experimental Group: Recording of concomitant medications

8.3 Weeks 2, 3, and 4

Control Group, home:

- Investigator uses standard of care to adjust Neupro dose as needed.
- Phone contact initiated by subject or Investigator as needed. Documentation of any contact or dosage adjustment.

Experimental Group, home:

- Subject uses Kinesia-360 at least on 2 consecutive days at home weekly to measure motor symptoms.
- Subject accesses Kinesia-360 motor symptom reports on device following each day of measurements.
- Investigator receives Kinesia-360 motor symptom reports via web portal following each day of measurements.
- Investigator combines standard of care with weekly Kinesia-360 motor symptom reports to adjust Neupro dose as needed.
- Phone contact initiated by subject or Investigator as needed and dispatch of Kinesia-360 motor symptom reports. Documentation of any contact or dosage adjustment.
- Recording of concomitant medications and Neupro dose via APP.
- A reminder phone call from the site to the subject each week during Weeks 2, 3, and 4 to ensure the subject will perform the protocol-requested Kinesia-360 assessments on 2 consecutive days per week. In addition, the subject should be reminded to charge the device and phone batteries the night prior to assessments.

8.4 Week 5 up to Week 12

Control Group, home:

- Treatment of subjects as per standard of care.
- Phone contact initiated by subject or Investigator as needed. Documentation of any contact or dosage adjustment.

Experimental Group, home:

- A reminder phone call from the site to the subject during the week prior to Visit 2 to ensure the subject will perform the protocol-requested Kinesia-360 assessments on 2 consecutive days. In addition, the subject should be reminded to charge the device and phone batteries the night prior to assessments.
- Optional: Subject may use Kinesia-360 as desired between Week 5 and Visit 2 (Week 12).
- Subject receives Kinesia-360 motor symptom reports on device following each day of measurements.

- Investigator receives Kinesia-360 motor symptom reports via web portal and by email following each day of measurements.
- Treatment of patients as per standard of care and dispatch of any Kinesia-360 motor symptom report.
- Phone contact initiated by subject or Investigator as needed and dispatch of Kinesia-360 motor symptom reports. Documentation of any contact or dosage adjustment.

